4.3 Secondary Objectives

To compare the three intervention alternatives (GEN, E-GEN, and TAU) with respect to:

- MDD symptoms;
- Changes to initial prescribing based on availability of pharmacogenomics data;
- Response rates to psychotropic medication;
- Remission rates;
- Time to response/remission;
- Medication side effects, including weight gain;
- Health-related quality of life;
- Physician's attitude and experience to DNA testing;
- Healthcare resource utilization and productivity losses;
- Total estimated healthcare costs associated with the treatment and management of patients;
- Cost-effectiveness of the GEN and E-GEN technology relative to TAU

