6.2.1 Inclusion Criteria

1. 18 years of age or older;
2. Suffer from a Major Depressive Episode meeting Diagnostic and Statistical Manual of Mental Disorders, Fourth Edition, Text Revision (DSM-IV-TR) criteria;
3. Have had an inadequate response within the current episode to at least one psychotropic treatment (listed in Appendix I). Inadequate response is defined as inadequate efficacy after 6 weeks of a psychotropic treatment or discontinuation of a psychotropic treatment due to adverse events (AEs) or intolerability;
4. Have each a screening and baseline score on the 16-item Clinician Quick Inventory of Depressive Symptomatology (QIDS-C₁₆) and 16-item Self-Report Quick Inventory of Depressive Symptomatology (QIDS-SR₁₆) rating scales ≥ 11 ;
5. Be able to understand the requirements of the study and provide written informed consent to participate in this study;
6. Agree to abide by the study protocol and its restrictions and be able to complete all aspects of the study, including all visits and tests.

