8.2 Secondary Outcome Measures

8.2.1 Clinical Outcome Measures of MDD Symptoms and Medication Side Effects

i. 16-Item Self-Report Quick Inventory of Depressive Symptomatology (QIDS-SR16)

The QIDS-SR16 is a patient reported measure designed to assess the severity of depressive symptoms(17, 18). The scale assesses the nine DSM-IV criteria symptom domains for major depression: sad mood, concentration, self-outlook, suicidal ideation, involvement, energy/fatigability, sleep disturbance (4 items: initial, middle, late insomnia, and hypersomnia), appetite/weight increase/decrease (4 items), and psychomotor agitation/retardation (2 items) (see Appendix III).

ii. 9-Item Patient Health Questionnaire (PHQ-9)

The PHQ-9 consists of nine questions, rated 0–3 according to the increased frequency of difficulty experienced in each area covered. Scores are self-rated by patients, with a possible range of 0–27, are summed and can then be interpreted as follows: no depression (0), minimal (1–5), mild (6–9), moderate (10–14), moderately severe (15–19), or severe (>20) depression (see Appendix IV).

iii. Generalized Anxiety Disorder 7-Item (GAD-7) Scale

The GAD-7 is a brief measure of symptoms of anxiety, based on diagnostic criteria described in DSM-IV(19). It consists of seven questions and is calculated by assigning scores of 0, 1, 2, and 3, to the response categories of “not at all”, “several days”, “more than half the days,” and “nearly every day,” respectively (see Appendix V).

iv. Clinical Global Impression (CGI)

The Clinical Global Impression Scale (CGI) is a brief clinician-rated instrument that consists of three different global measures (see Appendix VI):

- Severity of illness: overall assessment of the current severity of the patient's symptoms (CGI-S);
- Global improvement: overall comparison of the patient's baseline condition with his current state (CGI-I);
- Efficacy index: overall comparison of the patient's baseline condition to a ratio of current therapeutic benefit and severity of side effects (CGI-EI).

v. Changes to initial prescribing based on availability of pharmacogenomic data

The influence of pharmacogenomic data on a physician's initial prescription for both GEN and E-GEN will be evaluated by documenting the psychotropic medication prescribed before the availability of the pharmacogenomics data. This will be compared to changes (if any) to the physician's prescription when pharmacogenomics data becomes available.

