 - An additional aliquot of blood will be collected and stored for future pharmacogenomic research at the CAMH laboratories (see Appendix XVI, Part b). The sample will be de-identified, but matched to clinical data with the unique patient identification number.
- Collect urine sample for drug screen;
 - Urine samples will be collected for drug screening (barbiturates, cannabinoids, cocaine, and opiates).

- Any abnormal blood laboratory value must be assessed, with written notation, by the Investigator. If an abnormal laboratory value is clinically significant, the Investigator must immediately contact the medical monitor to discuss the patient's continued eligibility in the trial.
- Collect information on physician's prescription (including any changes) to patient's psychotropic medication based on information available at this visit;
- Collect information on history of prior pharmacogenomics testing;
- Collect information on current or recent (30 days) enrollment in other studies;
- Evaluate patient against the inclusion/exclusion criteria.

After signing an informed consent form (ICF), the patient has 2 weeks to be evaluated for enrollment in the study. Although the Screening Visit window is 2 weeks prior to enrollment, it is preferable that the participant be assessed at least 3 days prior to enrollment since the genotype results and GeneSight report typically take 2 or 3 days to be issued after receipt of buccal swabs.

The Investigator should contact the medical monitor, as clinically necessary, if the rescheduled visit will extend the screening beyond 2 weeks.

Patients' psychotropic medication should not be modified (in terms of type and dosage) during the screening period (i.e. between the Screening and Baseline visits), except for treatment with benzodiazepines.

Each patient will be assigned a unique patient identifier (UPI). At the Screening Visit, each patient will be assigned a screening number upon signing the ICF. All screening numbers will be assigned by the site in strict numerical sequence and no numbers will be skipped or omitted (e.g., each patient will be assigned to the lowest screening number available). The UPI will be on all case report form (CRF) pages.

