9.3 Baseline Visit (Visit 2)

Within 14 days of Screening Visit, the baseline assessment visit for the study will be completed.

Prior to any change or adjustment in antidepressant medication, the following will be evaluated and recorded:

- Psychiatric or quality of life evaluations:
 - QIDS-SR₁₆
 - HAM-D₁₇ (Central rater)
 - CGI-S (Treating clinician)
 - PHQ-9
 - GAD-7
 - EQ-5D-5L
 - SF-36
- Patient demographics;
Patients' date of birth, age, gender, ethnicity, height (without shoes), annual income, highest education, and health insurance coverage will be recorded.
- Medical and psychiatric history;
- The complete medical history will be conducted with a review of all body systems and the patient's past and concurrent illnesses, drug use (including urine drug test), alcohol use, drug allergies, and family medical history. Particular attention will be paid to past psychiatric history, in particular age at first depressive episode, frequency of relapses, response to previous treatments, and other concomitant psychiatric disorders and their treatment.

- Past and current psychotropic medications including response; The generic name of the psychotropic medication, the doses used, start and end date, as well as response to treatment (efficacy and AEs) will be recorded.
- Past (within three months) and current concomitant non-psychotropic medications (including nicotine replacement and smoking cessation medications); The generic name of the medication, the doses used, start and end date will be recorded.
- Smoking status and amounts
- Weight (without shoes, with clothes) and waist-to-hip ratio
- Changes (if any) to physician's prescription of psychotropic medication based on availability of pharmacogenomics data in GEN and E-GEN
- PIP-FQ
- UKU side effect rating scale
- FIBSER
- AEs
- Medication adjustments (including dose changes, switching, augmentation and discontinuation)
- Health resource utilization and productivity losses

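### The prescribing-change outcome is defined before versus after the report in GEN and E-GEN only, although the objective promises a three-arm comparison and the SAP does not analyse it

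*Protocol*

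**What the plan says.** The protocol describes this outcome in four places.

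- **Objective (4.3).** The list opens with "To compare the three intervention alternatives (GEN, E-GEN, and TAU) with respect to" and includes "Changes to initial prescribing based on availability of pharmacogenomics data". TAU is therefore part of the stated comparison.
- **Outcome definition (8.2.1 v).** "The influence of pharmacogenomic data on a physician's initial prescription for both GEN and E-GEN will be evaluated by documenting the psychotropic medication prescribed before" (meaning before any report). Then: "This will be compared to changes (if any) to the physician's prescription when pharmacogenomics data becomes available". TAU is not named, and the contrast is within patient.
- **Screening visit (9.1).** For every patient, before any report: "Collect information on physician's prescription (including any changes) to patient's psychotropic medication based on information available at this visit".
- **Baseline visit (9.3).** "Changes (if any) to physician's prescription of psychotropic medication based on availability of pharmacogenomics data in GEN and E-GEN". TAU is again left out.

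The schedule in Section 9.0 has a row for this outcome, marked at screening and baseline, and a row for medication adjustments that starts at baseline. Neither is restricted by arm.

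SAP 1.2 states that it replaces the protocol's analysis plan. Its objectives (2.1), endpoints (2.2) and analyses (5.2) do not include changes to initial prescribing. The prescribing measure it does analyse is congruence, tested between GEN and TAU by chi-square (5.2) and defined in 7.4.

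**The concern.** Taken alone, the definition in 8.2.1 v treats a before-after difference in the tested arms as the influence of the pharmacogenomic data. In this population that is unsafe. Entry requires the following: "Have had an inadequate response within the current episode to at least one psychotropic treatment (listed in Appendix I"). Participants must still be symptomatic at baseline (QIDS scores of at least 11, Protocol 6.2.1), and 9.1 says "Patients' psychotropic medication should not be modified (in terms of type and dosage) during the screening period", benzodiazepines excepted. Baseline is therefore the first planned decision point after a hold, in patients whose treatment has not worked or was not tolerated. Some of them would have a drug or dose changed there with no report at all.

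The result is meant to inform guidelines and a health technology application (SAP 1.1). An uncontrolled rate of prescribing change could be read there as the effect of the test, although a randomised no-report arm exists to supply the background rate.

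**Working it through.** **Which arms and which contrast**

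| Place | Arms | Contrast |
|---|---|---|
| Protocol 4.3 | GEN, E-GEN, TAU | between arms |
| Protocol 8.2.1 v | GEN, E-GEN | before vs after report |
| Protocol 9.3, baseline item | GEN, E-GEN | change based on report |
| Protocol 9.0, schedule rows | no restriction | data collection only |
| SAP 2.1, 2.2, 5.2 | outcome absent | none |

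The objective and the definition cannot both stand, and the SAP does not settle which applies.

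**Does congruence fill the gap?** Under SAP 7.4 a patient is congruent if every drug is green or yellow, and incongruent if any is red. A switch between two green drugs, or a dose change on one drug, alters the prescription and leaves congruence as it was. The chi-square in SAP 5.2 also names only GEN and TAU. Congruence is a controlled analysis, but of a different question.

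**Can TAU serve as control?** Yes. Protocol 7.1.3 withholds the TAU report from the treating clinician until at most 28 days before the 12-month completion. The screening prescription and the baseline medication adjustments are recorded without restriction by arm.

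**Size of the possible overstatement.** The plan states no change rate, so there is no figure to reproduce. The rates below are assumptions.

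- t = proportion whose prescription would change at baseline without a report
- g = additional proportion changed because of the report
- c = share of the background changes already written into the screening record as planned, and counted as part of the earlier prescription

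Raw before-after rate = (1 − c)t + g. Controlled difference = g. Overstatement = (1 − c)t, which is at most t.

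Upper limit, c = 0. Share due to the report = g/(t + g). The 95% half-width of the controlled difference is 1.96 × √{[(t + g)(1 − t − g) + t(1 − t)]/190}, with 190 per arm from Protocol 10.0:

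| t | g | Raw rate | Share due to report | Half-width (points) |
|---|---|---|---|---|
| 30% | 10% | 40% | 25% | 9.5 |
| 30% | 20% | 50% | 40% | 9.6 |
| 50% | 10% | 60% | 17% | 10.0 |
| 50% | 20% | 70% | 29% | 9.6 |
| 70% | 10% | 80% | 12.5% | 8.6 |
| 70% | 20% | 90% | 22% | 7.8 |

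Example of the half-width, t = 50% and g = 10%: 1.96 × √[(0.60 × 0.40 + 0.50 × 0.50)/190] = 1.96 × √(0.49/190) = 0.0995.

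Effect of the screening record, at t = 50% and g = 10%:

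- c = 0: 50 + 10 = 60%, overstatement 50 points
- c = 0.5: 25 + 10 = 35%, overstatement 25 points
- c = 1: 0 + 10 = 10%, overstatement nil

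The overstatement is also nil if t = 0. It therefore runs from zero to t, and the text does not fix c.

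**Is the controlled comparison informative?** With 190 per arm, two-sided 0.05 and background rates of 20%, 40% or 60%, power is 50–62% for a 10-point difference, 84–91% for 15 points and 98–99% for 20 points. Protocol 9.1 allows for participants found ineligible at baseline after randomisation, so 190 is a ceiling and real precision will be somewhat lower.

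**The case against.** The strongest reply is that the plan does not set up an uncontrolled analysis at all. It has three parts.

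1. **TAU is in the plan.** Objective 4.3 names TAU and the schedule rows apply to every participant. This stands. A reader of 8.2.1 v alone might infer that the trial has no TAU control for prescribing change. The documents do not support that: the control is promised and its data are collected. It is missing from the definition, from the 9.3 item and from any analysis.
2. **The screening record may already remove the background.** The item in 9.1 covers the prescription with any changes, on what is known before the report. On a natural reading it holds what the clinician would do without the test, so each patient's own pre-report decision would absorb much of the background change. This stands in part. Section 8.2.1 v does not say whether a change planned but held counts as the earlier prescription. It is therefore not established that the raw rate is inflated by the entire TAU change rate; that is the upper limit.
3. **No before-after estimate is scheduled.** The SAP governs and contains none, and the prescribing analysis it does contain uses the randomised control. This also stands: one cannot say that the trial will report a biased figure. The same fact means that objective 4.3 has no planned analysis, and the only method described anywhere for it is the uncontrolled one.

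The attributable shares above also rest wholly on assumed rates. They show scale and are not evidence of bias.

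**Conclusion.** The finding is an inconsistency with a possible bias attached. Protocol 8.2.1 v and 9.3 restrict the outcome to GEN and E-GEN, before versus after; Protocol 4.3 promises three arms; the SAP omits it.

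If a raw before-after rate were reported, it would overstate the report's influence by at most the TAU change rate, and by less, possibly nothing, if planned changes are captured at screening and counted as the earlier prescription. The documents give no change rate, so the size is unknown. Under assumed background rates of 30–70% and an added effect of 10–20 points, the report would account for about 13–40% of the counted changes in the worst case.

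This is one secondary outcome about prescribing. It does not touch the HAM-D17 primary analysis, and nothing is lost in data collection. The change is worth making because it is cheap and lets the trial answer its own objective with a randomised comparison.

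**What to change.** - **Protocol 8.2.1 v.** Define the outcome identically in all three arms: any difference in drug, dose or number of drugs between the pre-report prescription recorded at screening and the prescription set at the baseline visit.
- **Same section.** State whether changes planned at screening count as part of the earlier prescription. This also decides whether a report that redirects an already planned switch is counted as a change.
- **Protocol 9.3.** Remove the restriction of the item to GEN and E-GEN.
- **SAP 2.1, 2.2 and 5.2.** Add the outcome, with GEN vs TAU and E-GEN vs TAU as risk differences with 95% confidence intervals. Say that these two contrasts are reported whatever the arm-combining rule in SAP 2.1.2.2 selects. Keep congruence as a separate measure.

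The cost is protocol and SAP wording and one further analysis. No new data are needed, because the screening prescription and the baseline medication adjustments are already recorded in every arm. The downside for the sponsor is that the reported effect on prescribing is likely to be smaller than a raw before-after rate.

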8.2.2 Clinical Outcome Measures of Health Related Quality of Life

i. EuroQol (EQ-5D-5L)

The EQ-5D is designed for self-completion and assesses health across five domains: mobility, self-care, usual activities, pain/discomfort, and anxiety/depression. In the 5-level versions of EQ-5D (EQ-5D-5L), each domain has five levels of severity; health 'today' is assessed (See Appendix IX). The EQ Visual Analogue scale (EQ VAS) is a single 20 cm vertical visual analogue scale, with a range of 0 to 100, where 0 is the worst and 100 is the best imaginable health.

ii. Short Form (36) Health Survey (SF-36)

The SF-36 is a generic health status profile measure, consisting of eight dimensions: physical functioning, role-physical, bodily pain, general health, vitality, social functioning, role-emotional and mental health(25). These eight dimensions produced separate scores by taking a simple summation of individual item responses, and applying a linear transformation, in order to place them onto a 0 to 100 scale (see Appendix X).

8.2.3 Economic Outcome Measures

i. Healthcare Resource Utilization and Productivity Losses

Resource utilization and productivity losses incurred by GEN, E-GEN and TAU patients will be captured throughout the study. Information to be collected includes: physician visits (general practitioners, psychiatric, and other specialties), hospital utilization (psychiatric and non-psychiatric), emergency department visits (psychiatric and non-psychiatric institutions), medication use (antidepressants, antipsychotics, and other medications), and laboratory tests. For patients employed at the beginning of the study, productivity losses will be captured. This includes absenteeism (the number of days out of work) and number of disability claims (both short and long term) filed.

Participants will complete an economic questionnaire to capture healthcare resource utilization and productivity losses. Since participants may differ in terms of their baseline resource utilization, the questionnaire will be administered at baseline to document historical resource utilization, over the 3 months preceding, the intervention. Appropriate unit costs for Ontario will then be assigned to the data collected in order to provide an indication of the relative costs associated with receiving GEN, E-GEN and TAU.

Data on patient health care resource utilization will also be collected by the Institute for Clinical Evaluative Sciences (ICES). ICES is a research institute in Ontario that is a secure and confidential repository for publicly-funded administrative health data. Data on physician visits, hospitalizations, emergency department visits, and drug costs covered by the Ontario Drug Benefits (ODB) program are available for all Ontario residents and costs are accessible at the individual level through use of an encrypted health card number. Primary data collected from the study will also be linked via health card number, encrypted at ICES, to the ICES administrative databases for patients who had consented to data linkage. As before, costs associated with health services utilization will be based on utilization described above, with standard unit costs for Ontario as a multiplier.

The costs information captured (from economic questionnaire and ICES) will be used to conduct the economic evaluation of introducing GEN and E-GEN as compared to TAU. A trial-based economic evaluation will be conducted by comparing 1-year costs and outcomes associated with the different treatment arms. Since various treatments are compared in this analysis, an efficiency frontier will be created by ranking all options by costs and effectiveness. Any treatments dominated by other treatments having lower costs and higher efficacy will be eliminated from the analyses. In addition, any strategy dominated through the

principle of extended dominance will also be eliminated. Extended dominance rules out any intervention that is dominated by a linear combination of other strategies which produce greater benefit at a lower cost. The remaining options will form the efficiency frontier and incremental cost-effectiveness ratios will be calculated by comparing each option to the next one. Sampling uncertainty will be dealt by bootstrapping costs and effects. The short term results of the trials will be extrapolated to a longer time horizon (e.g. 5 years) by developing a decision analytic model (e.g. Markov model). A probabilistic analysis will be conducted to account for the uncertainty in the model parameters and modeling assumptions will be tested using sensitivity analyses. For both the trial-based and modeling-based economic evaluations, a cost-effectiveness plane will be used to present the results and show the efficiency frontier. Multiple cost-effectiveness acceptability curves will be used for presenting the results of the trial- and model-based economic evaluations.

8.2.4 Other Outcome Measures

i. Pharmacogenetics in Psychiatry Follow-Up Questionnaire (PIP-FQ)

The PIPFQ is a questionnaire (developed by CAMH) to evaluate physicians' attitude and experience to pharmacogenetics testing (see Appendix XI). Information is solicited from the physician on the processing of the physician's last referral, and for the entire study at 12 months.

9.0 STUDY TIME SCHEDULE

Study evaluation measures will be obtained over a 1-year period and will consist of seven scheduled assessments, not including screening and enrollment (Figure 1). Assessment visits will occur at baseline, 4 weeks, 8 weeks, 12 weeks, 6 months, 9 months and 12 months following randomization. The short-term follow-up visits will occur up to and including 12 weeks with the assessment of the primary outcome at 8 weeks, followed by long-term study visits at 6, 9 and 12 months. The following outlines the evaluations to be completed at each of the visits.

Figure 1. Study Time Schedule

Time Point	STUDY PERIOD								Early Termination Visit (ET)
	Screening/ Randomization - t1 (Visit 1)	Baseline t0 (Visit 2)	Short-term visits			Long-term follow-up			
			Week 4 (Visit 3)	Week 8 (Visit 4)	Week 12 (Visit 5)	Month 6 (Visit 6)	Month 9 (Visit 7)	Month 12 (Visit 8)	
ENROLLMENT									
Informed consent	x								
Eligibility screening	x								
Randomization	x								
Eligibility baseline		x							
INTERVENTIONS									
GeneSight Psychotropic (GEN)			_____	_____	_____	_____	_____	_____	
Enhanced GeneSight Psychotropic (E-GEN)			_____	_____	_____	_____	_____	_____	
Treatment as usual (TAU)			_____	_____	_____	_____	_____	_____	
ASSESSMENTS									
Buccal swab for genotyping	x								
Vital signs	x								
Mini International Neuropsychiatric Interview (MINI) for Axis 1	x								
Diagnostic and Statistical Manual of Mental Disorders, Fourth Edition, Text Revision (DSM-IV-TR) criteria for MDD	x								
DSM-IV-TR criteria for current substance use disorder	x								
Phlebotomy for laboratory panel	x								
Biobank sample	x								
Urine sample for drug screen and laboratory panel	x								
16-item Clinician Quick Inventory of Depressive Symptomatology (QIDS-C ₁₆)	x								
16-item Self Report Quick Inventory of Depressive Symptomatology (QIDS-SR ₁₆)	x	x	x	x	x			x	x
Changes to initial prescribing based on availability of pharmacogenomic data	x	x							
Medical history and psychiatric history	x	x							
Psychotropic medication history (current and past) and response	x	x							
Past (within one month) concomitant non-psychotropic medications	x	x							
Current concomitant non-psychotropic medications	x	x	x	x	x	x	x	x	x
Demographics, Employment, Insurance		x							
Smoking status and amounts		x	x	x	x			x	x
Height		x							
Weight and waist-to-hip ratio		x	x	x	x			x	x
Adverse events (AEs)		x	x	x	x			x	x
Pharmacogenetics in Psychiatry Follow-Up Questionnaire (PIPFQ)		x							x
17-item Hamilton Depression Rating Scale (HAM-D ₁₇)		x	x	x	x	x	x	x	x
9-item Patient Health Questionnaire (PHQ-9)		x	x	x	x			x	x
Generalized Anxiety Disorder 7-Item (GAD-7) Scale		x	x	x	x			x	x
Clinical Global Impression of Severity (CGI-S)		x			x			x	x
Clinical Global Impression of Improvement (CGI-I)					x			x	x
Clinical Global Impression Efficacy Index (CGI-EI)					x			x	x
Udvalg for Kliniske Undersogelser (UKU) side effect rating scale		x	x	x	x			x	x
Frequency, Intensity, and Burden of Side Effects Ratings (FIBSER)		x	x	x	x			x	x
EuroQol (EQ-5D-5L)		x			x	x	x	x	x
Short Form (36) Health Survey (SF-36)		x			x	x		x	x
Healthcare resource utilization and productivity losses		x	x	x	x	x	x	x	x
Current psychotropic medication and psychotropic medication trials since last visit		x	x	x	x	x	x	x	x
Medication adjustments (including dose changes, switching, augmentation and discontinuation)		x	x	x	x			x	x
Medication compliance: Morisky 8-item and BARS			x	x	x	x	x	x	x

